16.1.4.3. Multiple Imputation with Copy Reference

Missing data will also be explored assuming an MNAR approach. MNAR assumes the missing values depend on unobserved outcomes even after accounting for the observed data. Therefore, subjects cannot be modelled based on subjects with observed data, and more assumptions are needed. Copy reference is a type of MNAR approach where each missing value for subjects in the treatment group will be imputed using observed data in the placebo group, and missing values for subjects in the placebo group will be imputed under the MAR approach.

The following steps will be implemented:

Step 1**Step 1 (a)**

Intermittent missing data (before discontinuation from study) at each scheduled visit will be imputed, separately for each treatment group, under the MAR assumption using a multivariate normal imputation model and the Markov Chain Monte Carlo (MCMC) method with multiple chains. The number of imputations will be 40. The resulting data will have a monotone missing data pattern. The imputed data will be used together with the observed data to impute postdiscontinuation missing values.

Step 1 (b)

Only after Step 1a is completed, the remaining monotone missing data after discontinuation will be imputed using the FCS predictive mean matching method based on data from the placebo group only. The RB, SF, ES, and PGA subscores, stratification variables, a binary variable indicating if a subject is a treatment failure, and biomarker measurements (ALC, FCP, hs-CRP, log-transformed) at each planned visit will be included in the imputation model.

Step 2

Same as Step 2 described in Section 16.1.4.1.

Step 3

Same as Step 3 described in Section 16.1.4.1.

Step 4

Same as Step 4 described in Section 16.1.4.1.

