16. EFFICACY OUTCOMES

Unless otherwise stated, the primary efficacy analyses will be based on subject stratum used at the time of randomization for the FAS with Baseline MMS 5 to 9. Primary and key secondary efficacy analyses will be repeated for all subjects in FAS with Baseline MMS 4 to 9 as a supplementary analysis. The following definitions will be used to assess efficacy outcomes:

- Clinical response: A ≥ 2 -point and $\geq 30\%$ decrease from Baseline in MMS, and a ≥ 1 -point decrease from Baseline in RB subscore or an absolute RB subscore ≤ 1
- Clinical remission: SF subscore = 0 (or = 1 with a ≥ 1 -point decrease from Baseline), RB subscore = 0, and ES ≤ 1 (excluding friability)
- Endoscopic improvement: ES of ≤ 1 (excluding friability)
- Endoscopic normalization: ES = 0
- Mucosal healing: ES of ≤ 1 (excluding friability) with histologic remission measured by a Geboes Index score < 2.0
- Symptomatic remission: SF subscore = 0 (or = 1 with a ≥ 1 -point decrease from Baseline) and RB subscore = 0
- Complete symptomatic remission: SF subscore = 0 and RB subscore of 0
- Symptomatic response: Decrease from Baseline $\geq 30\%$ in composite RB and SF subscores
- Noninvasive clinical response: A $\geq 30\%$ decrease from Baseline in composite RB and SF, and a ≥ 1 -point decrease from Baseline in RB subscore or an absolute RB subscore ≤ 1
- Histologic improvement: Geboes Index score ≤ 3.1
- Histologic remission: Geboes Index score < 2.0
- Histologic improvement using Roberts Histopathology Index (RHI): $\geq 50\%$ reduction from Baseline in RHI or RHI ≤ 3
- Histologic remission using RHI: RHI ≤ 3 , with scores of 0 (zero) for both Geboes Grade 2B (lamina propria neutrophils) and Grade 3 (neutrophils in epithelium)
- Histologic improvement using Nancy Histologic Index (NHI): ≥ 1 point reduction from Baseline NHI
- Histologic remission using NHI: ≤ 1

- Clinical remission using total Mayo Clinic score: total Mayo Clinic score of ≤ 2 points with no individual subscore of > 1 point
- Clinical response using total Mayo Clinic score: $A \geq 3$ -point and $\geq 30\%$ decrease from Baseline in total Mayo Clinic score, and a ≥ 1 -point decrease from Baseline in RB subscore or an absolute RB subscore ≤ 1
- Corticosteroid-free clinical remission: Clinical remission at Week 52 and who had not been receiving corticosteroids for ≥ 12 weeks prior to Week 52
- Sustained clinical remission: Clinical remission at both Week 12 and Week 52
- Loss of response:

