16.1.4.1. Multiple Imputation Under MAR

Any missing component scores of MMS at the planned assessments will be imputed using multiple imputation under MAR. MAR assumes the missing value is independent of unobserved outcomes given observed data (eg, subjects with missing RB subscores can be modeled based on subjects with observed RB subscores) (Rubin 1987).

The following steps will be implemented:

Step 1

Regardless of the arbitrary missing data pattern (ie, non-monotone or monotone), a fully conditional specification (FCS) method with predictive mean matching for continuous variables will be used to impute the missing data at all timepoints. The FCS method allows for separate conditional distributions for each imputed variable. The predictive mean matching approach creates a regression model using parameters sampled from the posterior distribution and then a predicted value for each missing value is computed. The missing value is replaced by randomly selecting an observation from a set of 'k' values that are the closest predicted values to the missing predicted value. Missing data imputation will be performed using the SAS PROC MI procedure. The number of imputations will be 40 and is based on a projected overall dropout rate of 50% and relative efficiency of ~ 99%. A separate imputation model will be used for each treatment group. The RB subscore, SF subscore, ES, PGA, stratification variables, a binary variable indicating if a subject is a prior UC treatment failure of oral 5-ASA only (ie, subject had an inadequate response, loss of response, or intolerance to previous treatment with oral 5-ASA and did not have an inadequate response, loss of response, or intolerance to any other previous UC medication), Geboes index score, and biomarker measurements (absolute lymphocyte count [ALC], fecal calprotectin [FCP], hs-CRP, log-transformed) at each planned visit will be included in the imputation models. Refer to [Appendix 3](#) for the order of variables and timepoints in the model.

Step 2

For each of the imputed datasets at Week 12 and Week 52, subjects will be classified as responder or nonresponder based on the criteria specified in Section 16. For each dataset, the proportion of responders will be calculated. For endpoints requiring MMS, MMS will be recomputed by summing the scores of ES, SF, and RB.

Step 3

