16.1.4.2. Tipping Point Analysis

A tipping point approach based on multiple imputation of values through Week 12 and Week 52 will be used with a specified adjustment (referred to as delta adjustment or shift) applied to values imputed under a MNAR-based imputation model. To find a tipping point, a series of imputations will be performed with increasing values of delta.

The goal is to evaluate the plausibility of the assumed expected values for missing outcomes on each treatment group under which the conclusions change, ie, under which values of delta there are no longer evidence of significant treatment difference.

The following steps will be implemented:

Step 1

Same as Step 1 described in Section [16.1.4.1](#).

Step 2

Impute missing RB, SF, and ES subscores, then apply a random shift under the MNAR assumption to the imputed subscores and rounded to the nearest integer at Week 12 and Week 52 in both treatment groups, so that the expected value of the additive shift in RB, SF, and ES subscores combined is delta. The same variables used in Step 1 will be used in the MNAR model. The tipping point analysis sample code is specified in [Appendix 3](#). After the shift, if any assessments have values less than 0, the value will be set to 0. Similarly, if any assessments have values greater than 3, the value will be set to 3. MMS will then be rederived for each of the 40 imputed datasets, using the shifted values. Next, classify subjects as a responder or nonresponder at Week 12 and Week 52 based on the criteria specified in Clinical Study Protocol APD334-301 Section 10.5. For each dataset, the proportion of responders and nonresponders will be calculated.

Step 3

Same as Step 3 described in Section 16.1.4.1.

Step 4

Same as Step 4 described in Section 16.1.4.1.

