16.2.4. Sensitivity Analysis of Key Secondary Efficacy Variables

For the key secondary endpoints of endoscopic improvement, symptomatic remission, and mucosal healing, the sensitivity analyses described in Section 16.1.4 will be used.

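### The Copy Reference analysis leaves Geboes out of its variable list although it is planned for mucosal healing, and its readable text gives no rounding or range rule for normal draws of 0–3 scores

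*SAP*

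**What the plan says.** SAP 16.1.4.3 (Copy Reference) works in two imputation steps. Step 1(a) handles intermittent gaps, separately by treatment group, "under the MAR assumption using a multivariate normal imputation model and the Markov Chain Monte Carlo (MCMC) method with multiple chains". It names no variables. Step 1(b) then says that "the remaining monotone missing data after discontinuation will be imputed using the FCS predictive mean matching method based on data from the placebo group only". Its variable list reads: "The RB, SF, ES, and PGA subscores, stratification variables, a binary variable indicating if a subject is a treatment failure, and biomarker measurements" (lymphocytes, calprotectin and hs-CRP, log-transformed). Steps 2 to 4 are taken over from 16.1.4.1.

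Step 2 of 16.1.4.1 reads: "subjects will be classified as responder or nonresponder based on the criteria specified in Section 16". For clinical remission, Section 16 requires an SF of exactly 0 (or exactly 1 with a fall from Baseline) and "RB subscore = 0, and ES ≤ 1 (excluding friability"). For mucosal healing it requires ES ≤ 1 and a Geboes score below 2.0.

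The two neighbouring analyses are specified differently. Section 16.1.4.1 uses predictive mean matching throughout, and its variable list includes "Geboes index score, and biomarker measurements (absolute lymphocyte count [ALC" and the other biomarkers). Section 16.1.4.2 goes on to "apply a random shift under the MNAR assumption to the imputed subscores and rounded to the nearest integer", and then sets values below 0 to 0 and values above 3 to 3.

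On scope, Section 16.2.4 states: "For the key secondary endpoints of endoscopic improvement, symptomatic remission, and mucosal healing, the sensitivity analyses described in Section" 16.1.4 apply. Table 3 lists MI, MI-CR and NRI + MI for mucosal healing. The running text of 16.2 names only endoscopic improvement and symptomatic remission for sensitivity analyses.

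**The concern.** Copy Reference is the only reference-based check on the co-primary endpoints; the tipping point analysis is delta-based. It should show what happens when missing outcomes are drawn under its stated assumptions.

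Two gaps stand in the way. An endpoint that depends on Geboes is assigned to a model whose list does not impute Geboes. And RB, SF and ES, which take the values 0, 1, 2 and 3, are imputed from a continuous distribution and then tested against exact integers.

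The last paragraph of 16.1.4.1 allows the imputation model to be changed after unblinding, with the change described in the CSR. If either gap is found at that stage, the repair would be chosen with treatment known.

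**Working it through.** **The plan's own figure.** Section 16.1.4.1 bases 40 imputations on 50% projected dropout and about 99% relative efficiency. Taking 50% as the fraction of missing information, 1/(1 + 0.5/40) = 0.9877, which agrees. No other figure is stated for the imputation, and this point disputes none.

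**Geboes.** Protocol 9.8.1.2 takes biopsies at each endoscopy, so a subject with no endoscopy has neither ES nor Geboes. Under the Step 1(b) list ES is imputed and Geboes is not.
- ES imputed as 2 or 3: not healed, whatever Geboes is.
- ES imputed as 0 or 1: healing depends on Geboes < 2.0, which is missing. The listed variables give no classification, and 16.1.4.3 states no fallback.

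A subject with an observed ES ≤ 1 but no readable biopsy is in the same position.

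**RB and SF in Step 1(a).** For a normal draw, P(draw = 0) = 0 whatever the mean and SD; 1,000,000 simulated draws at each of 12 settings gave none. What a rule would give depends on the rule:
- rounding to the nearest integer and limiting to 0–3: P(RB = 0) = P(draw < 0.5) = Φ((0.5 − mean)/SD);
- limiting alone, with negative draws set to 0: P(RB = 0) = Φ(−mean/SD).

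The documents give no mean or SD for RB. Assuming means of 0.3–1.5 and SDs of 0.6–1.0:

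| Mean, SD | No rule | Limit only | Round and limit |
|---|---|---|---|
| 0.3, 0.6 | 0 | 0.309 | 0.631 |
| 1.0, 0.8 | 0 | 0.106 | 0.266 |
| 1.5, 0.6 | 0 | 0.006 | 0.048 |

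**ES in Step 1(a).** The criterion is an inequality, so some draws pass. Assume ES 0/1/2/3 = 10/20/40/30%.
- Mean = 0.20 + 0.80 + 0.90 = 1.90. Variance = (0.20 + 1.60 + 2.70) − 1.90² = 0.89, so SD = 0.943.
- Unrounded: Φ((1 − 1.90)/0.943) = 17%.
- Rounded: Φ((1.5 − 1.90)/0.943) = 34%.
- True: 10% + 20% = 30%.

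These are marginal probabilities; the actual model conditions on other scores.

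**Effect on the Week 12 difference.** Section 7 assumes 18.5% against 6.0%, a difference of 12.5 points, with 280 and 140 subjects. Suppose a share x in each arm has an intermittently missing Week 12 RB, would have remitted at the arm's planned rate, and is forced to nonresponse. The difference becomes 12.5 × (1 − x), and 280 × 0.185 × x etrasimod and 140 × 0.06 × x placebo remitters are lost.

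| x | Difference (points) | Etrasimod remitters lost | Placebo remitters lost |
|---|---|---|---|
| 1% | 12.375 | 0.5 | 0.1 |
| 2% | 12.25 | 1.0 | 0.2 |
| 5% | 11.875 | 2.6 | 0.4 |
| 10% | 11.25 | 5.2 | 0.8 |

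**The case against.** On rounding, the SAP is silent; it does not say that draws stay unrounded. Appendix 3, to which 16.1.4.1 and 16.1.4.2 refer for model order and sample code, is redacted, and redacted text may not be counted as missing. Protocol 9.4.2 defines the RB and SF subscores as rounded integers, so a programmer would probably round. All of this stands, and it makes the rounding point conditional. It does not remove it: 16.1.4.3 itself does not refer to Appendix 3, and the table above shows that the result depends on which rule is used.

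The reach is also limited. Section 16.1.4 defines intermittent missingness by a later observed value, so Week 52 is largely outside it, apart perhaps from a completer who lacks a Week 52 component. Step 1(b), which carries the reference-based assumption, uses donor values; non-integer Week 12 placebo values from Step 1(a) could become donors, but that is secondary. Two consecutive diary days within seven are enough for RB and SF, so those gaps should be uncommon in subjects still on study. Subjects who stop for worsening or take rescue are already known nonresponders under 16.1.2.

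On Geboes, ES > 1 settles nonresponse without it, Step 1(a) names no variables at all, and the SAP's general default for a missing binary outcome is nonresponse. That default could be used as a fallback. But applying it inside a multiple imputation would fix the histology half of the endpoint at failure, and 16.1.4.3 does not say that this is intended.

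**Conclusion.** Both parts hold on the readable text, and both concern a sensitivity analysis. The Geboes omission is the firmer one: it is a stated list that does not serve an endpoint assigned to it, and it does not depend on the rounding question. The rounding gap holds unless a rule exists in Appendix 3. If none does, an intermittently missing RB or SF counts as nonresponse in all 40 datasets, and an intermittently missing ES passes too rarely (17% against a true 30% in the assumed example).

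A reader might infer that RB = 0 can never occur in this analysis, that Copy Reference collapses to nonresponder imputation, or that it cannot be run for mucosal healing. The documents do not support these readings. Values imputed after discontinuation come from donors, an unrounded ES can still pass, any ES above 1 classifies mucosal healing, and a rounding rule may be redacted.

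The size rests on an intermittent-missing rate that the documents do not give: over an assumed 1–10%, the Week 12 difference falls from 12.5 to between 12.4 and 11.3 points. The primary CMH analysis already counts these subjects as nonresponders and does not change.

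**What to change.** 1. Add the Geboes index score to the Copy Reference model in Steps 1(a) and 1(b), and list the Step 1(a) variables. Otherwise remove MI-CR for mucosal healing from Table 3 and Section 16.2.4. In either case bring the running text of 16.2 into line with Table 3 and 16.2.4.
2. In Step 1(a), replace the multivariate normal model by the predictive mean matching of 16.1.4.1, within treatment group. The alternative is to round RB, SF and ES draws to the nearest integer and limit them to 0–3, as 16.1.4.2 does. Matching is preferable: it returns observed score values, and it also covers Geboes, for which a 0–3 integer rule would not fit because Section 16 uses cut-offs such as 3.1.
3. If Appendix 3 already contains a rounding rule for this step, refer to it in 16.1.4.3.

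The cost is a few sentences of SAP text and a small programming change, made before unblinding. No new data are needed, and neither the sample size nor the primary analysis changes.

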1.3. Benefit/Risk Assessment

Considering the significant unmet need for safe and effective, orally administered treatments for UC, etrasimod may potentially provide therapeutic benefit via S1P receptor modulation.

Adverse events that have been reported with S1P receptor modulators include bradycardia at the first dose or atrioventricular (AV) block, macular edema, hypertension, headache, cough, dyspnea, back pain, influenza, and diarrhea.

Safety and tolerability of etrasimod has been evaluated in Phase 1 studies with healthy adult subjects at single doses up to 5 mg and repeated doses up to 4 mg once daily. Repeated doses of 2 mg have been evaluated in Phase 2 studies of subjects with moderately to severely active UC (refer to the current edition of the IB). Etrasimod was found to be safe and well tolerated in these studies, with no clinically significant safety concerns with respect to vital signs, electrocardiograms (ECGs), pulmonary function tests (PFTs), ophthalmoscopy, or clinical laboratory tests. Etrasimod produced a dose-dependent sustained decrease in total lymphocyte count, which is expected given etrasimod's mechanism of action. Lymphocyte counts were within normal limits by 7 days after the last dose.

Detailed information regarding the known and expected benefits and risks and reasonably expected adverse events of etrasimod can be found in the IB.

Based on the mechanism of action of etrasimod and prior experience with other agents acting via a similar mechanism, monitoring for specific safety parameters are planned for this study, which include: auscultation of the lungs as part of the physical exam; PFT, exclusion of subjects with macular edema or retinopathy, with assessment of optical coherence tomography (OCT) occurring throughout the study; and exclusion of subjects with certain cardiac risks, with assessment of vital signs in the period following dosing.

- Auscultation of lungs will be conducted as part of the physical examination.
- Prospective subjects with a history of macular edema or retinopathy will be excluded from the study. All randomized subjects will be assessed by OCT at study entry, periodically throughout the treatment period, and as clinically indicated any time during the study.

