9.8.4. Efficacy-Related Biomarkers

Samples for biomarker assessments will be collected according to the Schedules of Assessments (Table 7 and Table 8). Blood, tissue, and stool samples will be analyzed by the central or specialty laboratory. Details for collection, processing, and storage will be provided in the Laboratory Manual. Residual samples will be stored and may be used for additional analyses if the subject has granted consent where allowed by the regulatory authorities and local ethics committees.

C-reactive protein (CRP): CRP is an acute phase protein expressed by hepatocytes in response to inflammatory cytokines and will be assessed using a hs-CRP assay. Investigators will be blinded to the hs-CRP results during the treatment and follow-up periods.

Fecal calprotectin: Fecal calprotectin is a complex consisting of calcium-binding proteins. It is expressed by activated neutrophils (and to a lesser extent by macrophages and monocytes) and fecal levels correlate with the number of neutrophils in the gut. It is used as a biomarker of intestinal inflammation. Investigators will be blinded to the fecal calprotectin results during the treatment and follow-up periods.

Lymphocyte counts: Etrasimod is believed to modulate lymphocyte trafficking resulting in a reduction in peripheral lymphocyte count and lymphocyte availability for recruitment to sites of inflammation. During the treatment period, the Investigator will be blinded to the white blood cell (WBC) and differential counts during the treatment and follow-up periods. During the

treatment period, WBC differential results will be assessed by an unblinded Medical Monitor (not providing direct medical oversight of study conduct). If either of the following occur, the unblinded Medical Monitor will notify the Investigator with additional instructions.

- ANC < 1000 cells/ μ L
- ALC < 200 cells/ μ L

If the ANC is confirmed below the 1000 cells/ μ L limit, the Investigator will be requested to closely monitor for serious infection and institute appropriate follow-up at his or her discretion.

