- An assumption of data missing at random (MAR) within each treatment group will be investigated. Missing data, eg, component scores of MMS at the planned assessment timepoints, will be imputed using multiple imputation methodology ([Rubin 1987](#)) under the MAR assumption. Binary responder-type endpoints will subsequently be computed from observed and imputed data and analyzed using the same method as in the primary analysis. Continuous endpoints will be analyzed using analysis of covariance based on observed and imputed values.
- A tipping point analysis will be performed for the primary and key secondary endpoints by considering all possible combinations of the number of responders and nonresponders among subjects with missing data in each treatment group. The results of analysis for all possible combinations will be summarized graphically, depicting a boundary between combinations that result in a statistically significant treatment effect versus not statistically significant. Clinical plausibility of the combinations on the boundary will be discussed in the clinical study report to evaluate robustness of study conclusions to missing data.
- A mechanism of missingness not at random will be investigated for subjects with missing data. These subjects, regardless of the randomized treatment group, will be assumed to have a similar distribution of outcomes after discontinuation as subjects with available data in the placebo group. This is akin to modeling the missing outcomes as if the subjects continued on their background therapy only and accounting for the study effect observed in subjects on placebo. This will be implemented using a multiple imputation approach of Copy Reference to impute missing values, eg, component scores of MMS at the planned assessment timepoints.

Complete descriptions of the sensitivity analyses and detailed multiple imputation method and procedures will be provided in the SAP prior to database lock.

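### The Copy Reference imputation model includes post-baseline lymphocyte counts, which etrasimod lowers directly, so the outcomes it imputes for etrasimod dropouts need not be placebo-like

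*SAP*

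**What the plan says.** Protocol 10.4 sets the target for this analysis. Subjects with missing data, in either arm, "will be assumed to have a similar distribution of outcomes after discontinuation as subjects with available data in the placebo group", and the protocol likens this to patients who stay on background treatment alone.

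SAP 16.1.4.3 builds it in two parts. Step 1(a) fills intermittent gaps separately by arm. Of the result, the SAP says "The imputed data will be used together with the observed data to impute postdiscontinuation missing values". In Step 1(b) the remaining post-discontinuation values are "imputed using the FCS predictive mean matching method based on data from the placebo group only". The listed predictors are the Mayo components, PGA, the stratification variables, a treatment-failure indicator and the biomarkers: "biomarker measurements (ALC, FCP, hs-CRP, log-transformed) at each planned visit will be included in the imputation model". Nothing in the readable text re-centres ALC or limits it to Baseline.

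On the drug's effect, Protocol 1.3 says "Etrasimod produced a dose-dependent sustained decrease in total lymphocyte count", and Protocol 9.8.4 says etrasimod is believed to "modulate lymphocyte trafficking resulting in a reduction in peripheral lymphocyte count". On recovery, Protocol 1.3 says "Lymphocyte counts were within normal limits by 7 days after the last dose".

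**The concern.** A reference-based imputation asks what would have happened had the subject been like a placebo subject. Here the regression is learned from placebo subjects, whose ALC varies for ordinary reasons. It is then evaluated at ALC values that the drug has pushed down. Whatever ALC slope the placebo data yield, real or chance, is multiplied by that drug-induced gap and applied in the same direction to every etrasimod subject with an on-treatment count. The suppressed count also describes a state that ends shortly after dosing stops, whereas the outcomes being imputed come after discontinuation.

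Copy Reference is the only planned reference-based check on the Week 12 and Week 52 coprimary results. Under SAP Table 3 it is repeated for endoscopic improvement, symptomatic remission and mucosal healing. As specified, it could look better or worse than a placebo-like assumption warrants, for a reason unrelated to efficacy.

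**Working it through.** **The plan's own figures.** The documents give no figure for the ALC effect. Two related figures reproduce closely:
- Relative efficiency of 40 imputations at 50% missing: 1/(1 + 0.5/40) = 98.8% (SAP 16.1.4.1 says about 99%).
- Fisher's exact power at Week 52, 280 vs 140, 23.5% vs 10.0%, one-sided 0.025: 92.8% by exact enumeration (SAP 7 says 93.4%).

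The 10% placebo rate is the target used below.

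**Step 1: how far off-support is ALC?** Shift in placebo SDs = ln(1 - r)/s, where r is the fractional fall and s the placebo SD of log ALC. Both are assumed: r = 20%, 40%, 60%; s = 0.3 to 0.5. At s = 0.4:
- r = 20%: ln(0.8)/0.4 = -0.56 SD
- r = 40%: ln(0.6)/0.4 = -1.28 SD
- r = 60%: ln(0.4)/0.4 = -2.29 SD

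Over s = 0.3 to 0.5 the shifts are 0.4-0.7, 1.0-1.7 and 1.8-3.1 SD below the placebo mean.

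**Step 2: effect on the predicted score.** Shift × standardised partial slope. At slope 0.2 and s = 0.4: 1.28 × 0.2 = 0.26 SD for a 40% fall; 2.29 × 0.2 = 0.46 SD for a 60% fall.

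**Step 3: effect on imputed remission.** A simulation used placebo-fitted predictive mean matching with 5 donors per match, 40 imputations, 100 placebo subjects, 60 etrasimod dropouts, s = 0.4 and 300 trials per cell. The later score (higher = worse) was 0.3 × baseline score + 0.4 × on-treatment score + slope × ALC + error, with remission set at 10% in placebo. Dropouts' own scores were drawn as placebo, so only ALC differed. Mean imputed remission, with / without on-treatment ALC in the model:

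| Assumed slope | 20% fall | 40% fall | 60% fall |
|---|---|---|---|
| -0.2 | 7.7 / 9.8% | 6.0 / 9.2% | 4.3 / 9.5% |
| -0.1 | 8.7 / 9.7% | 7.8 / 9.4% | 7.0 / 9.5% |
| 0 | 9.6 / 10.0% | 9.8 / 9.9% | 10.4 / 9.7% |
| +0.1 | 10.3 / 9.7% | 11.7 / 9.6% | 13.9 / 9.9% |
| +0.2 | 11.6 / 9.7% | 13.9 / 9.5% | 18.4 / 9.4% |

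Monte Carlo error is at most 0.069/√300 = 0.4 points. Without on-treatment ALC, every cell lies between 9.2% and 10.0%. A positive slope (higher ALC, worse score) favours etrasimod; a negative slope works against it.

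**Step 4: slope zero.** The mean holds, but the between-imputation variance rises: 0.00222/0.00118 = 1.9 times at a 60% fall and 0.00156/0.00120 = 1.3 times at 40%. The estimated slope still has chance error of roughly 1/√n, and the ALC gap multiplies it.

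**Step 5: arm-level effect.** Assuming 60 of 280 etrasimod subjects are imputed, at a 60% fall: (60/280) × (4.3 - 9.5) = -1.1 points; (60/280) × (18.4 - 9.4) = +1.9 points.

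**The case against.** The strongest reply is that Copy Reference conditions on a subject's own history by design, and the protocol names that method. RB, SF, ES, FCP and hs-CRP may also be treatment-affected, so some departure from the marginal placebo distribution is inherent. That stands, and dropping ALC does not remove it. But those variables measure symptoms, mucosa or inflammation, for which a placebo-fitted relation has meaning at the observed value. ALC is the one listed predictor that the drug shifts directly.

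Other points also stand in part:
- Predictive mean matching draws only observed placebo scores, so the distortion lies in which donors are picked, not in free extrapolation. The simulation already includes this.
- Missing ALC after discontinuation would itself be imputed from placebo, so the problem concerns on-drug values only.
- The simulation uses one on-treatment ALC visit and omits FCP, hs-CRP, PGA and the strata. How far the full model dilutes the effect is untested.
- Appendix 3, which SAP 16.1.4.1 cites for the order of variables and timepoints, is redacted and may hold relevant detail.

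A reader might infer that a large share of this test's power is lost, by taking the SAP's 50% as the fraction imputed. The documents do not support that. The number of imputations is "based on a projected overall dropout rate of 50"%, an overall projection. SAP 16.1.2 counts discontinuation for worsening, lack of efficacy or UC-related adverse events, and rescue, as known nonresponse. Those subjects are not imputed.

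**Conclusion.** The mismatch is real but modest in consequence. As written, the model evaluates placebo-fitted equations at drug-suppressed ALC, so imputed etrasimod outcomes need not match the distribution that Protocol 10.4 describes.

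A reader might go further and conclude that the imputed outcomes are definitely not placebo-like, or that the error favours etrasimod. Neither follows. Bias in the mean requires an ALC-outcome association in placebo given the other predictors, and the documents give neither its size nor its sign. With no association, imputed remission stays at 9.6-10.4% and only imputation variance grows. The ranges in the working rest on assumed falls, SD, slopes and numbers imputed; they illustrate sensitivity and do not predict this trial.

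Only the Copy Reference analyses are affected. The primary analysis uses nonresponder imputation and alone gates the key secondary tests (SAP Table 3, note a). The MAR model is fitted by arm, and the tipping-point analysis reuses that step. The tipping-point analysis therefore remains a check on missing-not-at-random departures that does not share this problem.

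**What to change.** In SAP 16.1.4.3 Step 1(b), state that Baseline ALC is retained and post-baseline ALC is removed from the Copy Reference imputation model. FCP and hs-CRP can stay as disease markers. Leave the by-arm MAR model in 16.1.4.1 unchanged.

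The cost is one line of SAP text and a small change to the variable list in the program. The downside is losing one predictor, which matters only as far as ALC carries outcome information in placebo. SAP 16.1.4.1 allows changes to the imputation model after unblinding, but this one is foreseeable and is better fixed beforehand.
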